6.3. Sample Size and Accrual

The study design is to enroll 400 healthy adult participants ages 18 to 60 that reside in CHIKV endemic areas. Randomization will equally allocate subjects to vaccine or placebo schedules with stratification by ages 18-40 and 41-60 years. The enrollment plan does not include provision for replacing subjects with incomplete injections or visit schedules.

Enrollments may occur rapidly at more than one site. The data management CRO will carefully monitor study enrollment and notify all sites and the VRC Protocol Chair when the completion of enrollment is near.

The sample size for this study was not selected to test a formal null hypothesis. It reflects the number of vaccine doses that are available for the study and the desire to gain maximal information for the conduct of possible Phase 3 follow on trials. This latter consideration is particularly important as reliable estimates of CHIKV incidence in the target population, vaccine effects and logistical considerations in implementing future trials must be understood prior to a Phase III trial. Nevertheless, power computations are provided below as an indication of the probability of observing results of interest.

There are not good data to estimate the loss to follow-up rate for this study. The power calculations assume a 10% loss in both groups for the primary and secondary endpoints. Loss to follow-up for the exploratory outcomes are likely to be larger but are not included as power calculations are not included for these outcomes.

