7 STUDY SUBJECTS

7.1 Subject Disposition

Table 14.1.1 (Appendix I), will present a summary of the reasons that subjects were screened but not enrolled.

The composition of analysis populations, including reasons for subject exclusion, by treatment arm, is presented in **Table 14.1.2, Appendix I**.

The disposition of subjects in the study will be tabulated by site and treatment group (**Table 14.1.3, Appendix I**). The table shows the total number of subjects screened, enrolled, receiving at least 1 dose, receiving at least 2 doses, discontinued dosing or terminated from study follow-up and the number completing the study. CHIKV infection status and subject disposition will be tabulated by site and treatment group (**Table 14.1.4, Appendix I**). The table shows the number and percentages of subjects who had a PCR-confirmed CHIKV infection, those with a clinical CHIKV infection (both further split by when infection occurred), and those uninfected.

A flowchart showing the disposition of study subjects, adapted from the CONSORT Statement [3] will be included (**Figure 14.1.1, Appendix II**). This figure will present the number of subjects screened, enrolled, lost to follow-up, and analyzed, by treatment arm where applicable.

A listing of subjects who discontinued dosing or terminated from study follow-up and the reason will be included in **Listing 16.2.1 (Appendix III)**.

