10 ANALYSES OF CHIKUNGUNYA INFECTION INCIDENCE AND TIME TO EVENT

Analyses of CHIKV infections are exploratory. A few definitions of incident cases exist and therefore efficacy will be considered in:

- cases for which CHIKV is confirmed by a positive PCR
- cases with symptoms consistent with CHIKV but not necessarily confirmed by a positive PCR

Efficacy will include all cases using 2 exploratory alternatives for case inclusion:

1. all infections post dose 1 (Day 0),
2. all infections post dose 2.

Subjects not receiving dose 2 will be included in definition 1.

The analysis of efficacy is divided into two parts which are described below, using the intent-to-treat cohort.

Clinical cases as well as PCR confirmed cases are listed in **Listing 16.3.1, Appendix III**. Individual time to event data post dose one and post dose two are listed in **Listing 16.3.2 -16.3.3, Appendix III**.

10.1 Description of Observed Events:

- Incidence and number of clinical cases of CHIKV
 - Inclusion 1: All cases post dose 1 (Day 0)
 - Inclusion 2: All cases post dose 2. Subjects not receiving dose 2 will be considered for inclusion 1.
- Incidence and number of PCR confirmed cases of CHIKV
 - Inclusion 1: All cases post dose 1 (Day 0)
 - Inclusion 2: All cases post dose 2. Subjects not receiving dose 2 will be considered for inclusion 1.

For each scenario, incidence rates and number of cases will be described by treatment group by age stratum and aggregating and by combining age strata. Results are presented in **Tables 15.1.1-15.1.4 in Appendix I**.

10.2 Analysis of Vaccine Efficacy:

- Time to occurrence of clinical CHIKV infection
 - Inclusion 1: All cases post dose 1 (Day 0)
 - Inclusion 2: All cases post dose 2. Subjects not receiving dose 2 will be considered for inclusion 1.
- Time to occurrence of PCR confirmed CHIKV infection
 - Inclusion 1: All cases post dose 1 (Day 0)
 - Inclusion 2: All cases post dose 2. Subjects not receiving dose 2 will be considered for inclusion 1.

Time to event will be based on the date of onset of the clinical symptom (for clinical cases) or on blood sample with the first positive laboratory test indicating CHIKV infection (for PCR confirmed cases).

Time to occurrence post dose one and post dose two will be calculated for clinical CHIKV infections as well as PCR confirmed CHIKV infections as follows:

Post first injection:

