- For subjects with infection: First date of diagnosis of clinical CHIKV infection minus date of first injection + 1. These subjects will not be censored.
- For subjects with no infection: Date of study completion or date of early termination minus date of first injection + 1. These subjects will be censored at their date of study completion or date of early termination.

Post second injection:

- For subjects with infection: First date of diagnosis of clinical CHIKV infection minus date of second injection + 1. These subjects will not be censored.
- For subjects with no infection: Date of study completion or date of early termination minus date of second injection + 1. These subjects will be censored at their date of study completion or date of early termination.
- Subjects that do not receive the second dose are excluded.
- Subjects that develop CHIKV before second dose are excluded.

The principal exploratory analysis consists of a comparison between the vaccine and placebo groups of the time to occurrence of infection after first dose and after second dose. The magnitude of vaccine effect will be estimated in terms of vaccine efficacy (95% CI) obtained from Cox proportional hazard model. Statistical testing will be performed using Log-rank test. (**Tables 15.2.1-15.2.4, Appendix I**)

The secondary exploratory analysis consists of an adjusted survival for age and site using a Log-rank test. In addition to univariate adjustments, multivariate adjustment will be performed in a single model using Cox regression for time to infection after first dose and after second dose. Estimates of vaccine efficacy adjusting for baseline characteristics will be displayed in **Tables 15.3.1-15.3.4, Appendix I**. Kaplan-Meier survival curves will be plotted by group, as presented in **Figures 15.1.1-15.1.4 Appendix III**.

10.3 Sample SAS Code for Analysis:

Notations

Timevar = the variable that gives the time to occurrence

Censor_var = the variable defining whether timevar is censored

Trtmnt_group = treatment group where 0 = Placebo and 1=VRC-CHIKVLP059-00-VP;

Cox Proportional Hazard

SAS Code for Cox Regression to obtain Vaccine Efficacy and 95% CI for Vaccine Efficacy:

```
Proc phreg;
```

```
Model timevar*censor_var(0)=trtmnt_group (and any covariates)/rl;
```

```
Ods output parameterestimates=ests(keep=HazardRatio HRUpperCL HRLowerCL);
```

```
Run;
```

```
Ods output RiskDiffCol1=rde1;
```

```
Run;
```

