Pulse	Normal													
	Mild													
	Moderate													
	Severe													
	Potentially Life Threatening													
Temperature (°C)	Normal													
	Mild													
	Moderate													
	Severe													
	Potentially Life Threatening													

TABLE 14.3.6:
Number and Percentage of Subjects with Concurrent Medications by
Treatment Group <<Age Stratum>>

Medication	CHIKV (N=X)		Placebo (N=X)		All Subjects (N=X)	
	n	%	n	%	n	%
	x	x.x	x	x.x	x	x.x

TABLE 14.3.7:
Number of Pregnancies by Outcome and Treatment Group

	CHIKV (N=X)	Placebo (N=X)	All Subjects (N=X)
Total pregnancies	x	x	x
Live births			
Spontaneous abortions			
Elective abortions			
Ectopic pregnancies			
Stillbirths			

TABLE 15.1.1:
Incidence of Clinical Cases of CHIKV Post Dose One by Treatment Group and Stratified by Age

Age Stratum	CHIKV			Placebo		
	n	%	95%CI	n	%	95%CI
18-40	x	xx	xx-xx	x	xx	xx-xx
41-60						
Aggregate (18-60)						

Note: Subjects not receiving dose two are included in this table.
 n = number of subjects with CHIKV symptoms (clinical cases)
 % = n divided by the number of subjects receiving dose one
 95%CI = 95% Clopper-Pearson confidence interval.

TABLE 15.1.2:
Incidence of Clinical Cases of CHIKV Post Dose Two by Treatment Group and Stratified by Age

Age Stratum	CHIKV			Placebo		
	n	%	95%CI	n	%	95%CI
18-40	x	xx	xx-xx	x	xx	xx-xx
41-60						
Aggregate (18-60)						

n = number of subjects with CHIKV symptoms (clinical cases)

% = n divided by the number of subjects receiving dose two and free of infection when receiving dose two

95%CI = 95% Clopper-Pearson confidence interval.

Additional Tables using the same format as 15.1.1 and 15.1.2

TABLE 15.1.3:
Incidence of PCR Confirmed Cases of CHIKV Post Dose One by Group and Stratified by Age

TABLE 15.1.4:
Incidence of PCR Confirmed Cases of CHIKV Post Dose Two by Group and Stratified by Age

TABLE 15.2.1:

Primary Exploratory Analysis – Vaccine Efficacy for Time to Occurrence of Clinical CHIKV Infection Post Dose One

	CHIKV N= Placebo N=		
	V.E.	95% CI for V.E.	p-value
Primary Analysis: Unadjusted	x.xx	xx.xx - xx.xx	x.xxx

N=number of subjects in the specific treatment group that received first dose

V.E. =Vaccine efficacy obtained from Cox Proportional Hazard model

95%CI = 95% confidence interval obtained from Cox Proportional Hazard model

p-value = result of comparison of Kaplan-Meier survival curves between groups by Log-rank test.

TABLE 15.2.2:

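### CHIKV incidence is tabulated only as a crude proportion that counts dropouts as uninfected through Week 72; person-time and Kaplan-Meier incidence should be tabulated as well

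*Combined protocol and SAP*

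**What the plan says.** **Purpose.** Comparing CHIKV incidence between the arms is an exploratory objective. Protocol 6.3 goes further: among the things to be understood before a Phase 3 trial it lists "reliable estimates of CHIKV incidence in the target population", and it gives this as part of the rationale for the sample size. The same section assumes 10% loss for the primary and secondary endpoints and adds, without a figure, "Loss to follow-up for the exploratory outcomes are likely to be larger".

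**Protocol 6.4.4.** Infection is to be handled both as a yes/no outcome and as time to event. For each of the two, the protocol promises an infection rate per arm and vaccine efficacy, both with 95% intervals.

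**SAP 10.1 and Tables 15.1.1-15.1.4.** The text says "For each scenario, incidence rates and number of cases will be described by treatment group by age stratum". In the shells, the post-dose-one percentage is "n divided by the number of subjects receiving dose one" and the post-dose-two percentage is "n divided by the number of subjects receiving dose two and free of infection when receiving dose two". The interval is "95%CI = 95% Clopper-Pearson confidence interval". None of the four tables has person-time or a site row.

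**SAP 10.2 and Tables 15.2.x and 15.3.x.** The time-to-event tables show vaccine efficacy, its interval and a p-value. Kaplan-Meier curves are plotted by arm (Figures 15.1.1-15.1.4). For uninfected subjects the rule is: "These subjects will be censored at their date of study completion or date of early termination". The early-termination date is not defined.

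**By site.** SAP 7.1 states that "CHIKV infection status and subject disposition will be tabulated by site and treatment group". Table 14.1.4 gives n and %, including a row for subjects lost and not known to be infected.

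**The concern.** A proportion whose denominator is everyone dosed is a valid estimate of 72-week risk only if everyone is followed for 72 weeks or until infection. A subject lost at Week 5 stays in the denominator but cannot contribute a later case. The error therefore runs in one direction, and enrolling more subjects would not remove it. The percentage also carries no time unit, so a planner with a different follow-up length cannot rescale it without further assumptions.

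The estimator that does allow for dropout appears only as a curve. The time-to-event infection rate with an interval that protocol 6.4.4 promises has no table in the SAP. The placebo-arm figure, which Phase 3 planning would need most, would thus be tabulated only in the form that is biased downward.

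**Working it through.** **Inputs.** From the documents: 200 per arm; follow-up of 72 weeks (504 days); 10% loss for the primary and secondary endpoints; visits 8 weeks apart after Week 8. Assumed here: losses of 20% and 30%; a constant infection hazard; a true 72-week risk of 5% for illustration; dropout unrelated to infection risk.

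**The plan's own figure.** The documents state no expected CHIKV incidence and no power for it. The nearest figure that uses the loss input is in protocol Table 3 (SAP Table 2): 200 × 0.90 = 180, and 1 − 0.99^180 = 83.62%. This matches the printed value. It confirms the 10% input and says nothing about CHIKV.

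**Crude proportion against true risk.** Let I be the true 72-week risk, d the fraction who would leave before Week 72 if not infected first, and r the risk accrued by leavers before they go.

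Expected crude proportion = (1 − d)·I + d·r

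For small I, r/I is close to the mean leaving time t divided by 72, so the relative shortfall is close to d·(1 − t/72).

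- Evenly spread leaving (t = 36): d/2.
- All leave at Week 4: d·68/72.
- All leave at Week 64: d·8/72.

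| Loss d | Week 4 | Evenly spread | Week 64 |
|---|---|---|---|
| 10% | 9.4% low | 5.0% low | 1.1% low |
| 20% | 18.9% low | 10% low | 2.2% low |
| 30% | 28.3% low | 15% low | 3.3% low |

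Exact example at I = 5% with evenly spread leaving: the hazard over 72 weeks is −ln(0.95) = 0.0513, so r = 1 − 0.05/0.0513 = 2.52%. At 10% loss the crude figure is 0.90 × 5% + 0.10 × 2.52% = 4.75%. At 30% it is 0.70 × 5% + 0.30 × 2.52% = 4.26%.

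**Does Kaplan-Meier repair it?** In a simulation of 200,000 subjects with true risk 5% and censoring at last contact, one minus Kaplan-Meier gave 5.04% at 10% loss and 4.96% at 30%. The crude proportions in the same runs were 4.79% and 4.22%.

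**Sampling error.** The exact 95% interval for 10 cases in 200 is 2.4% to 9.0%.

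**Censoring date (a separate matter).** This does not touch Tables 15.1.x. With evenly spread leaving, mean observed time is 72·(1 − d/2): 68.4 weeks at 10% loss and 61.2 at 30%. If each leaver's termination date falls L weeks after last contact, and the Week 72 cap is ignored, the person-time rate is multiplied by 68.4/(68.4 + 0.1L) or 61.2/(61.2 + 0.3L).

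- L = 0: no bias.
- L = 8 (one visit interval): 1.2% to 3.8% low.
- L = 16: 2.3% to 7.3% low.
- Every leaver carried to Week 72: 5% to 15% low, which is the crude proportion's error again.

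**The case against.** The best defence is that Tables 15.1.x are only the yes/no half of a two-part plan. Kaplan-Meier curves by arm are planned for clinical and PCR-confirmed cases after each dose, and subject-level times are listed, so a planner could obtain a dropout-adjusted incidence. This largely stands: the plan does allow for censoring. But a curve with no tabulated value or interval does not deliver what protocol 6.4.4 promises. SAP 2.1 warns that some protocol analyses are left out, yet those it names are later immunogenicity time points and interim analyses, not the final CHIKV incidence.

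The second defence is size. At the only stated loss the bias is about 5% relative, sampling error is far larger, and both documents call the CHIKV analyses exploratory. That stands too and limits the priority.

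Four stronger readings are tempting and are not supported:

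- *That pooling sites pulls incidence down.* Pooling gives a size-weighted mean. It can hide differences between sites but does not lower the estimate.
- *That infections are not shown by site.* Table 14.1.4 shows them by site and arm. It lacks only intervals and person-time.
- *That the censoring rule is itself biased.* The early-termination date is undefined; if it equals last contact, the bias is zero. Subjects may also report symptoms and be tested between scheduled visits.
- *That Phase 3 would be underpowered.* Understated incidence would make a Phase 3 trial larger: by 1/0.95, about 5%, at 10% evenly spread loss.

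**Conclusion.** The point holds as a reporting gap with a known direction. The only tabulated CHIKV incidence is a crude proportion that is too low whenever uninfected subjects leave early: about 5% relative at 10% evenly spread loss (1% to 9% by timing), and about 15% (3% to 28%) at 30% loss. The 30% is an assumption, since protocol 6.3 says only that loss for these outcomes will probably exceed 10%. The sizes also rest on a constant hazard and on dropout unrelated to infection; in an outbreak the timing of cases relative to dropout would change them.

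Incidence is affected more than efficacy. If loss follows the same pattern in both arms, nearly the same factor applies to each and largely cancels from the relative risk. The censoring date is a secondary clarification that bears on the Kaplan-Meier and Cox results alone. Priority is modest because the analysis is exploratory and imprecise, but a removable one-way bias should not remain in the figure meant to inform Phase 3.

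**What to change.** 1. In Tables 15.1.1-15.1.4 keep the crude percentage and add, by arm and age stratum, (a) cases, person-years and cases per 100 person-years with an exact Poisson 95% interval, and (b) Week 72 Kaplan-Meier cumulative incidence with a 95% interval and the number still at risk. In the post-dose-two tables, count time from dose two and read the estimate at the matching point (504 − 28 = 476 days on the planned schedule).
2. Add site rows as description only. The shells show six sites, so with equal enrolment a site would have about 200/6 = 33 subjects per arm, and the intervals will be wide.
3. In SAP 10.2 state that uninfected subjects are censored at the last contact at which CHIKV status was assessed, and define the early-termination date accordingly.

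The cost is a few table columns and one derived date from visit and contact records. Somewhat less person-time may be credited. No new data collection is needed, and the design and the other analyses are unchanged.

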Calculate the following from the hazard ratios/estimates obtained from SAS

Vaccine Efficacy = 1 – Hazardratio;

Lower 95% CI= 1 – HRUpperCL which is the same as $1 - \exp(\text{estimate} + 1.96 * \text{stderr})$

Upper 95% CI= 1 – HRLowerCL which is the same as $1 - \exp(\text{estimate} - 1.96 * \text{stderr})$

Log-Rank Test

SAS Code for Log-Rank Test to obtain p-value:

```
Proc lifetest;
```

```
time timevar*censor_var(0);
```

```
strata trtmnt_group;
```

```
id pid;
```

```
Ods output homtests = tests(where=(test="Log-Rank") keep=test probchisq);
```

```
Run;
```

Obtain p-value from SAS: p-value=probchisq;

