Primary Exploratory Analysis – Vaccine Efficacy for Time to Occurrence of Clinical CHIKV Infection Post Dose Two

	CHIKV N= Placebo N=		
	V.E.	95% CI for V.E.	p-value
Primary Analysis: Unadjusted	x.xx	xx.xx - xx.xx	x.xxx

N=number of subjects in the specific treatment group that received **second** dose

V.E. =Vaccine efficacy obtained from Cox Proportional Hazard model

95%CI = 95% confidence interval obtained from Cox Proportional Hazard model

p-value = result of comparison of Kaplan-Meier survival curves between groups by Log-rank test.

Additional Tables using the same format as 15.2.1 and 15.2.2

TABLE 15.2.3:

Primary Exploratory Analysis – Vaccine Efficacy for Time to Occurrence of PCR Confirmed CHIKV Infection Post Dose One

TABLE 15.2.4:

Primary Exploratory Analysis – Vaccine Efficacy for Time to Occurrence of PCR Confirmed CHIKV Infection Post Dose Two

TABLE 15.3.1:

Secondary Exploratory Analysis - Vaccine Efficacy for Time to Occurrence of Clinical CHIKV Infection Post Dose One with Adjustment for Baseline Characteristics

	CHIKV N= Placebo N=		
	V.E.	95% CI for V.E.	p-value
Secondary Analysis: Multivariate adjustment for age, race, site	xx.x	xx.x – xx.x	x.xxx
Univariate Adjustments			
Age (18-40, 41-60)	xx.x	xx.x – xx.x	x.xxx
Race (White/Non-White)	xx.x	xx.x – xx.x	x.xxx
Site (1-6)	xx.x	xx.x – x.xx	x.xxx

N=number of subjects in the specific treatment group that received **first** dose

V.E. =Vaccine efficacy obtained from Cox Proportional Hazard model

95%CI = 95% confidence interval obtained from Cox Proportional Hazard model

p-value = for the multivariate adjustment, it is the result of comparison of Kaplan-Meier survival curves between groups by Log-rank test.

For univariate adjustment, it is the result of comparison of Kaplan-Meier survival curves between groups stratified by the adjusted variables by Log-Rank test.

TABLE 15.3.2:

Secondary Exploratory Analysis - Vaccine Efficacy for Time to Occurrence of Clinical CHIKV Infection Post Dose Two with Adjustment for Baseline Characteristics

	CHIKV N= Placebo N=		
	V.E.	95% CI for V.E.	p-value
Secondary Analysis: Multivariate adjustment for age, race, site	xx.x	xx.x – xx.x	x.xxx
Univariate Adjustments			
Age (18-40, 41-60)	xx.x	xx.x – xx.x	x.xxx
Race (White/Non-White)	xx.x	xx.x – xx.x	x.xxx
Site (1-6)	xx.x	xx.x – x.xx	x.xxx

N=number of subjects in the specific treatment group that received **second** dose

V.E. =Vaccine efficacy obtained from Cox Proportional Hazard model

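### In the exploratory CHIKV efficacy tables, the multivariate row's p-value, read literally, repeats the unadjusted one, and the SAP's only VE interval fails if an arm has no cases

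*Combined protocol and SAP*

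**What the plan says.** **Multivariate row.** SAP 10.2 states that "multivariate adjustment will be performed in a single model using Cox regression". The shells of Tables 15.3.1-15.3.4 take VE and its 95% CI from a Cox model, and the row is labelled "Multivariate adjustment for age, race, site". The footnotes then define three p-values:

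- Unadjusted Tables 15.2.x: "p-value = result of comparison of Kaplan-Meier survival curves between groups by Log-rank test".
- Multivariate row: "p-value = for the multivariate adjustment, it is the result of comparison of Kaplan-Meier survival curves between groups by Log-rank test".
- Univariate rows: "For univariate adjustment, it is the result of comparison of Kaplan-Meier survival curves between groups stratified by the adjusted variables by Log-Rank test".

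SAP 10.2 also says: "The secondary exploratory analysis consists of an adjusted survival for age and site using a Log-rank test". Race is not in that sentence. The sample Cox code in 10.3 ends with "Ods output parameterestimates=ests(keep=HazardRatio HRUpperCL HRLowerCL", so the model's own p-value is not kept. The sample log-rank code has treatment group as its only strata variable.

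**VE interval.** SAP 10.3 defines one interval. It begins "Lower 95% CI= 1 – HRUpperCL which is the same as" and continues with one minus the exponential of the estimate plus 1.96 standard errors, which is a Wald limit. Exact (Clopper-Pearson) intervals are named in Tables 15.1.x, but only for incidence within an arm. Protocol 6.4.4 treats infection both as yes/no and as time to event, and promises VE with a 95% CI for each; the yes/no version converts the relative risk. SAP section 10 and its shells contain only the time-to-event version.

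**The concern.** A p-value printed beside an adjusted VE and CI should belong to an adjusted comparison. Programmed as worded, this one would match the corresponding Table 15.2.x p-value on the same subjects and show nothing of the adjustment.

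The second gap arises when cases are few. If no vaccine recipient is infected, the VE tables would show a log-rank p-value with no usable interval. An interval could then be picked after the counts are known, when the candidates differ a good deal. Protocol 6.3 says the trial should inform incidence and vaccine effects before Phase III, so a reader would look for that interval.

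**Working it through.** **1. The p-value.** No arithmetic is needed; the three footnotes set side by side above are the evidence. The multivariate wording matches the unadjusted wording and lacks the stratification phrase that follows for the univariate rows. The sample code cannot settle the intent, because it has no stratified log-rank test even for the rows that plainly use one. The covariates conflict under either reading: age and site in 10.2; age, race and site in the shells.

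**2. The Wald interval with no vaccine cases.** Take 200 per arm (SAP 4.1; ITT cohort per SAP section 10), no vaccine cases, k placebo cases, no ties and no dropout. With b the log hazard ratio, the Cox log partial likelihood is, up to a constant, −Σ log(1 + 200·e^b/(200−j)), j = 0,…,k−1. It rises steadily as b falls, so it has no maximum. A fit for 0 v 6 stopped at log HR about −23 with SE about 44,000; the SAP formula then gives VE limits of minus infinity and 100%, beside a log-rank p of 0.014.

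**3. How often an arm has no cases.** The documents give no attack rate, so placebo rate r and VE are assumptions. P(at least one empty arm) = 1 − [1 − (1 − r(1−VE))^200]·[1 − (1−r)^200]. Example, r = 2%, VE 70%: vaccine arm empty 0.994^200 = 0.300; placebo arm empty 0.98^200 = 0.018; result 1 − 0.700 × 0.982 = 0.312.

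The narrower event of 0 vaccine and at least 4 placebo cases, where log-rank p is below 0.05 and no VE interval exists, has probability (1 − r(1−VE))^200 · P(Bin(200, r) ≥ 4).

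| Assumed placebo rate | 1% | 2% | 3% | 5% |
|---|---|---|---|---|
| Any empty arm, VE 70% | 61% | 31% | 17% | 5% |
| Any empty arm, VE 50% | 45% | 15% | 5% | 0.6% |
| 0 v ≥4, VE 70% | 8% | 17% | 14% | 5% |
| 0 v ≥4, VE 50% | 5% | 8% | 4% | 0.6% |

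**4. How far the candidate intervals differ.** Lower 95% VE limits for 0 v k, 200 per arm. Exact conditional: u = 1 − 0.025^(1/k), limit = 1 − u/(1−u); for k = 4, u = 0.602 and the limit is 1 − 1.515 = −51%. Score: the relative-risk score limit using the restricted maximum likelihood estimate. Profile: from the partial likelihood in step 2.

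| Cases | Exact | Score | Profile | Log-rank p |
|---|---|---|---|---|
| 0 v 3 | −142% | −27% | +11% | 0.082 |
| 0 v 4 | −51% | +5% | +39% | 0.045 |
| 0 v 5 | −9% | +24% | +54% | 0.025 |
| 0 v 8 | +41% | +53% | +73% | 0.004 |

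In these four cases the score limit falls on the same side of zero as the log-rank test falls of 0.05. With no vaccine effect and attack rates from 1% to 5%, full enumeration gives 5%-level rejection rates of 0.5% to 2.6% for the exact test, 4.0% to 4.8% for score, and 9.6% down to 5.5% for the likelihood ratio.

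**The case against.** - **The absence of stratification is inferred.** The footnote does not use the word unstratified. SAP 10.2 speaks of survival adjusted for age and site by a log-rank test, and the table titles refer to adjustment for baseline characteristics. The sample code is fragmentary. This stands: the footnote may be a drafting slip, and the point holds only on a literal reading. The covariate mismatch holds regardless.
- **Pairing a log-rank p-value with a Cox interval is the SAP's general convention.** This also stands. A reader might infer that the pairing itself is the error, or that it makes the multivariate row unusually discordant. The documents do not support that: SAP 10.2 chooses the log-rank test for the unadjusted analysis too. In a simulation with assumed site risks of 0.6% to 9%, VE 75% and 15% dropout (1,227 runs with cases in both arms), log-rank p and Wald CI disagreed at the 5% level in 10.0% of runs for the adjusted row and 11.2% for the unadjusted tables. Adjusting or not, with the Wald test held fixed, changed the result in 2.1%. The defect is one of labelling and specification more than of numerical conflict.
- **Clinical cases need not be PCR-confirmed.** This stands. Illness from other causes can count in both arms, so an empty arm is less likely in the clinical tables, and an assumed VE of 50% to 70% need not apply to them.
- **The omission is partly disclosed and other summaries survive.** SAP 2.1 says not all protocol analyses are detailed, 6.1 allows risk ratios with intervals, and the Preface requires deviations to be justified. A team could also report VE as not estimable. This stands in part. But 2.1 names only exploratory immunogenicity and interim analyses as left out, section 10 does set out the CHIKV analyses, and no passage names a method for the relative-risk interval.

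**Conclusion.** Both parts hold, at low severity. Read literally, the multivariate row of Tables 15.3.1-15.3.4 pairs an adjusted VE and CI with the unadjusted p-value, and the covariate list differs between SAP 10.2 and the shells. The SAP has no VE interval that works when an arm has no cases, and the relative-risk VE that the protocol promises is not carried over.

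The size of the second part rests on assumed attack rates of 1% to 5%, VE of 50% or 70%, 200 per arm and complete follow-up. The probabilities suit the PCR-confirmed tables better than the clinical ones, and they include counts too small for any method to be informative.

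A reader might go further and conclude that the trial's efficacy result would be uninterpretable. That does not follow: the analyses are exploratory with no order of primacy, and exact arm incidence and the log-rank test both survive an empty arm when the other has cases. The safety and Week 8 antibody conclusions do not depend on any of this.

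**What to change.** 1. **Multivariate row.** Report the treatment p-value from the same adjusted Cox model as the VE and CI, by adding it to the `keep` list in SAP 10.3 and rewording the footnote. To keep the log-rank convention instead, state a log-rank test stratified by the listed covariates. With two age groups, two race groups and six sites that means 2 × 2 × 6 = 24 strata, about 17 subjects each (400/24), so strata with subjects at risk in only one arm when a case occurs would add nothing.
2. **Covariates.** Make SAP 10.2 and the shells agree. The documents do not show which list is intended.
3. **Relative-risk VE.** Add VE = 1 − relative risk to section 10 and its tables, with one interval named in advance; the relative-risk score interval is a reasonable example. Report it whenever an arm has no cases. If only the placebo arm is empty, the finite VE limit is the upper one. If both are empty, report arm incidence only.

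The cost is a footnote, a code item, some SAP text and one extra table row. The score interval is approximate at very small counts; the exact interval is conservative and profile likelihood is anti-conservative there, which is why the choice should be fixed before the counts are known.
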